### 5.3 Method for Assigning Subjects to Treatment Groups

- After informed consent, randomization will occur as a tiered approach based on age (group 1 <12 years, group 2 ≥ 12 years) and Mini-ICARS score (group a score <25, group b ≥ 25 points) to give 50/50% to placebo/drug, respectively. If a Mini-ICARS was performed and recorded <1 year prior to enrollment, randomization can be based on that historic score. The randomization scheme will be generated by a statistician that is not part of the study team and will be provided to the applicable research pharmacy.

### 5.4 Preparation and Administration of Study Drug

- The study drug and placebo will be compounded by the research pharmacy at each institution.
- A member of the study team will pick up the drug/placebo from the pharmacy and deliver it to the investigator meeting with the patient. The investigator will educate the patient on proper administration of the drug/placebo (number of times per day to take the drug, amount for each administration) and answer any questions or concerns the patient/patient's parent or guardian may have. The study drug may also be mailed to subjects at their address of residence.
- The research pharmacy will obtain the study drug and have the production lab over encapsulate the drug and placebo for blinding purposes.

Table 2: Formulation of Acetazolamide and Placebo

ORAL CAPSULE FORMULATION	Acetazolamide 250 mg Capsules	Placebo Capsules
Active ingredient	Acetazolamide 250 mg tablets (any commercially available generic brand)	N/A
Empty Gelatin Size 0 capsules	TBD	TBD

Lactose USP powder	Quantity sufficient to fill capsule	Quantity sufficient to fill capsule
--------------------	-------------------------------------	-------------------------------------

## 5.5 Subject Compliance Monitoring

Subjects and/or their caregivers will be asked to keep a patient diary noting the date they take their study drug and any adverse events. They will be asked to bring their patient diary to each study visit along with all used and unused study drug containers.

If a subject is significantly non-compliant, as per the investigator's discretion, with the study drug regimen, the investigator will discuss with the patient the reasons that the drug is not being taken as requested. Missed doses will be recorded. If this discussion does not improve the subject's compliance to greater than 50% of the doses taken per week by the next study visit, they are encouraged to adhere to the study medication schedule.

## 5.6 Prior and Concomitant Therapy

- All concomitant medication and concurrent therapies (physical therapy (PT)/occupational therapy (OT)/speech therapy (ST)/feeding therapy (FT)) will be documented at baseline and at each visit (from 30 days prior to the first dose).
  - Medication trade name;
  - Indication for which the medication was given;
  - Dose/strength, route, and frequency of administration;
  - Date started and date stopped (or continuation at study exit).
- All medications that do not have a high risk of serious reactions will be permitted while on the study. Any medication listed as an exclusion criterion is not permitted while on the study (i.e., Mecamylamine, Sodium Phosphates, Salicylates, Mefloquine, Methenamine and other Carbonic Anhydrase Inhibitors).
- If a subject has started taking a prohibited medication on the exclusion criteria, they will be discontinued from the study. If a subject is started on a medication that has a high risk of serious reaction, continued participation in the study will be decided on a case-by-case-basis.

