#### **3.2 Number of Subjects**

We aim to enroll 26 evaluable patients. Up to 7 additional patients will be enrolled to account for a 20% loss in sample size due to ineligibility, major treatment violation, cancellation, or withdrawal prior to completion of the 6-month blinded phase of the study. Maximum projected accrual is, therefore, 33 patients. Enrollment will continue until the 26th evaluable patient completes the blinded phase. Enroll will pause when 26 patients have either completed or are

actively completing the blinded phase; enrollment will reopen if any of these patients withdraw before completing the blinded phase.

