## 6.10 Visit – Early Termination

- Procedural elements
  - Blood collection (same as section 6.1)
  - Urine collection (same as section 6.1)
- Medication adherence questionnaire (see section 6.2)
- Interview elements
  - AE assessment
  - Concomitant medication review
  - Ongoing therapies (same as section 6.1)
  - Reason for discontinuation of study treatment and discontinuation of study

- Study withdrawal – investigator will discuss with the patient and caretakers the reason for withdrawal from the study. Investigator will also attempt to consent/assent subject and/or caretaker family to collect follow up information whenever possible through review of medical records. Data to be collected include lab data to look at urinalysis values, chemistries in serum, hematology, physical exam data (including vital signs and reviewing concomitant medications), ICARS scoring, NPCRS scoring and any other adverse events if available. These evaluations will be obtained as part of their clinical care.

Table 3: Schedule of Events	Visit 1 (Wk 0)	Visit 2 (Wk 2-3)	Visit 3 (Wk 3-5)	Visit 4 (Visit 3 + 1-3 wks)	Visit 5 (Wk 21-34)	Visit 6 (Visit 5 + 1-3 wks)	Visit 7 (Visit 6 + 1-3 wks)	Visit 8 (Visit 7 + 1-3 wks)	Visit 9 (Wk 49- 105)	Early Withdrawal
Informed Consent	x									
Medical History	x									
Clinical History	x									
Physical Exam*	x				x				x	
HC	x			x	x			x	x	
Height	x			x	x			x	x	
Weight	x			x	x			x	x	
Vital Signs (Temperature, BP, RR, HR)	x				x				x	
Ophthalmological exam including intraocular pressure testing**									x	
NPCRS a	x				x				x	
Mini-ICARS b	x				x				x	
PATA	x				x				x	
Blood c collection	x	x	x	x	x	x	x	x		x
Urine d Collection	x	x	x		x	x	x		x	
PROMIS e	x				x				x	
I/E review; Randomization	x									
Dose Initiation	x									
Dose Adjustment		x	x	x		x	x	x	x	
Open label continuation or discontinuation					x					x
Medication adherence questionnaire		x	x	x	x	x	x	x		x
AE Assessment		x	x	x	x	x	x	x		x
Concomitant Medication Review	x	x	x	x	x	x	x	x		x
Ongoing therapies (PT, OT, ST, FT) f	x	x	x	x	x	x	x	x		x

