## Handling of Intercurrent Events

Per the E9(R1) guidance (*Statistical Principles for Clinical Trials; Addendum: Estimands and Sensitivity Analysis in Clinical Trials*), a treatment policy strategy will be used to address intercurrent events. That is, for the primary analysis, each patient's change in Mini-ICARS score from baseline to 6 months will be used regardless of whether an intercurrent event occurs.

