## Handling of Missing Data

Attempts to minimize missing data will be made through site training and data monitoring (e.g., form delinquency notifications, data queries). Patients who prematurely discontinue study treatment will be encouraged to remain in the study for their scheduled efficacy and safety assessments. The primary analysis evaluating the between-arm mean difference in the change in Mini-ICARS score from baseline to 6 months will include all patients with a baseline and 6-month Mini-ICARS score. For patients with a missing Mini-ICARS score at 6 months, imputation will be used as part of a sensitivity analysis. Specifically, all patients with a missing Mini-ICARS score at 6 months will be assumed to have no change in Mini-ICARS score from baseline to 6 months (i.e., 0 imputed for all missing change scores).

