## 7.3 Subject Populations for Analysis

- *Intent-to-treat set*: All randomized patients, regardless of whether they received their assigned study treatment.
- *Full analysis set*: All randomized patients who complete the baseline and 6-month visits.
- *Safety set*: All randomized patients who receive at least one dose of acetazolamide or placebo.
- *Per-protocol set*: All randomized patients who report taking at least 4 weeks of their assigned study treatment and complete the baseline and 6-month visits.

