### **Abnormal Laboratory Values**

A clinical laboratory abnormality should be documented as an adverse event if they meet the following criteria:

- Hepatic impairment defined as AST/ALT  $>3.0 - 5.0 \times$  ULN if baseline was normal;  $>3.0 - 5.0 \times$  baseline if baseline was abnormal
- Renal impairment defined as serum creatinine 1.5-1.9 times ULN for age OR  $\geq 26.5 \text{ umol/l}$  increase from ULN for age

If these values are noted and no other cause for these laboratory changes are likely, then drug will be stopped, and repeat labs will be obtained at reasonable intervals per investigator's clinical judgement after discontinuation until labs have normalized to stabilized. Treatment may be restarted if labs have returned to baseline using the same ramp up schedule as described for visits 2, 3 and 4. These changes in treatment will be documented.

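### Section 5.6 takes a patient who starts a barred drug off the study, which before Visit 5 forgoes the 6-month Mini-ICARS that the treatment policy strategy in Section 7.2 would use

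*Combined protocol and SAP*

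**What the plan says.** Section 5.6 (Prior and Concomitant Therapy) forbids the drugs named in the exclusion criteria during the trial and sets the consequence of starting one: "If a subject has started taking a prohibited medication on the exclusion criteria, they will be discontinued from the study".

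Section 7.2 has two paragraphs that bear on this. Under Handling of Intercurrent Events, the strategy is treatment policy: each patient's 6-month change in Mini-ICARS "will be used regardless of whether an intercurrent event occurs". Under Handling of Missing Data, "Patients who prematurely discontinue study treatment will be encouraged to remain in the study for their scheduled efficacy and safety assessments". In the sensitivity analysis for missing scores, "all patients with a missing Mini-ICARS score at 6 months will be assumed to have no change in Mini-ICARS score".

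Section 7.3 defines the full analysis set, on which the primary test is run, as "All randomized patients who complete the baseline and 6-month visits".

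The 6-month Mini-ICARS is done at Visit 5 (Section 6.5, weeks 21 to 34). Section 6.10 lists no Mini-ICARS for the early-termination visit, and the Mini-ICARS row of Table 3 is marked only at Visits 1, 5 and 9. After withdrawal, Section 6.10 provides for an attempt, with consent, to retrieve data from routine clinical records, including "ICARS scoring, NPCRS scoring and any other adverse events if available".

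Section 3.2 provides for replacement: "enrollment will reopen if any of these patients withdraw before completing the blinded phase".

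**The concern.** Starting a barred drug during the blinded phase is an intercurrent event. A treatment policy strategy needs the patient's 6-month score after that event, yet Section 5.6 ends the patient's participation before the score is taken. The retention sentence in Section 7.2 does not help, because it covers patients who stop study treatment, and Section 5.6 goes further than that.

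At stake is the match between what the primary analysis claims to estimate and the patients it contains. A randomized patient drops out of the comparison because of something that happened after randomization, and an assumed value stands in for the observed one in the sensitivity analysis.

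The event is plausible. Sodium bicarbonate is on the barred list in Section 4.2, Section 1.5 expects that acidosis may develop on acetazolamide, and the table of earlier studies records abnormally low bicarbonate in 9 of 24 patients in the PMM2-CDG pilot. The planned response to acidosis is a dose reduction, so this shows only that a barred drug could be started because of a treatment effect. It does not show how often.

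**Working it through.** **1. The plan's own figure.** Inputs from Section 7.1: expected decrease 6 points on acetazolamide and 1.68 on placebo, SD of change 4, two-sided alpha 0.05, power 75%.

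- Difference: 6 − 1.68 = 4.32.
- Noncentrality at 13 per arm: 4.32 / (4 × √(2/13)) = 2.75, with 24 degrees of freedom.
- Power from the noncentral t distribution: 75.2% at 13 per arm and 71.5% at 12 per arm.

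So 13 per arm (26 in total) is reproduced. The ceiling in Section 3.2 is too: 26 / 0.80 = 32.5, rounded up to 33.

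**2. Following one patient who starts a barred drug before Visit 5.**

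- Section 5.6: taken off the study.
- Section 6.10 and Table 3: early-termination visit without a Mini-ICARS. An ICARS score may exist in clinical records, but that is neither the scheduled assessment nor tied to the Visit 5 window.
- Section 7.3: no 6-month visit, so not in the full analysis set. The per-protocol set also requires that visit.
- Section 7.2: enters only the sensitivity analysis, with a change of 0.
- Section 3.2: enrollment may reopen, so the evaluable number is protected up to the ceiling of 33. The removed patient's outcome is not recovered.

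A patient who starts a barred drug after Visit 5 already has the 6-month score, so the primary endpoint is unaffected.

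**3. Effect on the sensitivity analysis.** Assume 13 observed patients per arm after replacement, at the planning means, plus *k* removed patients in one arm entered as 0. That arm's mean becomes (arm mean) × 13 / (13 + *k*).

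| Removed | Arm | Mean in that arm | Expected difference | Change from 4.32 |
|---|---|---|---|---|
| 1 | acetazolamide | 6 × 13/14 = 5.571 | 5.571 − 1.68 = 3.89 | −9.9% |
| 1 | placebo | 1.68 × 13/14 = 1.560 | 6 − 1.560 = 4.44 | +2.8% |
| 2 | acetazolamide | 6 × 13/15 = 5.200 | 5.200 − 1.68 = 3.52 | −18.5% |
| 2 | placebo | 1.68 × 13/15 = 1.456 | 6 − 1.456 = 4.54 | +5.2% |

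**4. Effect on the primary analysis.** This depends on a score that nobody would observe, so only a conditional range can be given. Suppose 1 of 13 acetazolamide patients is removed and the other 12 average a 6-point decrease. If the removed patient would also have improved by 6, the treatment policy difference is 4.32, the same as among completers. If that patient would not have changed, the arm mean is 6 × 12/13 = 5.54 and the treatment policy difference is 5.54 − 1.68 = 3.86, while the completer analysis still targets 4.32. The documents do not say which is nearer the truth.

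**5. Drug list.** The parenthesis in Section 5.6 names 6 entries. Section 4.2 names those 6 and 8 more, 14 in all; sodium bicarbonate is one of the 8.

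**The case against.** The best counter-argument is that Section 5.6 is loosely worded. Section 1.5 says that a patient who comes to meet exclusion criteria during the study will have treatment terminated, and taking a barred drug is an exclusion criterion. Read with the retention sentence in Section 7.2, such a patient might still be seen at Visit 5. But the sentence in Section 1.5 sits among laboratory checks, while Section 5.6 is the specific rule for barred drugs. Section 6.10 also records discontinuation of treatment and discontinuation of the study as separate matters, so the protocol distinguishes the two. A site following Section 5.6 as written would remove the patient.

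Other objections stand in part:

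- The table in the working describes the zero-change sensitivity analysis, not the primary estimate, and would look the same for a score missing for any other reason. It also assumes 13 observed per arm, whereas Section 3.2 replaces to a total of 26 without guaranteeing balance. It is an illustration.
- The frequency is unknown. Patients already on these drugs are excluded at entry, and the 20% allowance in Section 3.2 names major treatment violations and withdrawals. That allowance protects power but does not restore the outcomes.
- Section 8.1 is only a partial contrast. For hepatic or renal impairment, "then drug will be stopped, and repeat labs will be obtained at reasonable intervals", a restart is possible, and removal from the study is not mentioned. However, it does not mention Visit 5 either, and the risk/benefit text in Section 1.5 says that the major risks would lead to study withdrawal.
- Other routes lose the same score: withdrawal for non-adherence (Section 4.4), and unblinding, which ends the blinded portion (Section 5.7.1). Correcting Section 5.6 does not close these.

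**Conclusion.** The concern holds. Applied as written before Visit 5, Section 5.6 gives up a 6-month outcome that the plan's own treatment policy strategy calls for, and nothing else in the plan reliably recovers it. How many patients would be affected cannot be derived from the documents, and no direction of bias is claimed.

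With 13 patients per arm, single patients carry weight: under the stated assumptions, one removed patient moves the expected sensitivity result by −9.9% or +2.8%, depending on the arm. The conflict should be corrected because it is plain in the text and nearly free to remove. It does not undermine the sample size or the primary test. The shortened drug list in Section 5.6 is a minor consistency point, since that section already makes the exclusion criteria the governing rule.

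**What to change.** In Section 5.6, replace removal from the study with removal from study drug. Suggested wording: *A subject who starts a prohibited medication will be discontinued from study drug and encouraged to remain in the study; the Visit 5 Mini-ICARS and the safety assessments will still be collected.* This keeps the safety purpose of the rule and brings conduct into line with Section 7.2.

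As a minor correction, replace the six-drug parenthesis in Section 5.6 with a reference to the full list in Section 4.2. The Study Summary carries the same six drugs and can be aligned in the same amendment.

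The cost is a protocol wording amendment, with the usual IRB submission. Visit 5 is already scheduled, so no visit is added. The 26 evaluable patients, the ceiling of 33 and the two-sample t-test all stay as they are.

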## 5.7 Packaging

Packaging, labeling, taste, and appearance of test and control treatments will be very similar to maintain the blind. Active drug concentrations will be prepared by the pharmacy prior to handoff to clinicians or families for administration. Both the study drug and comparator will be labeled with the same label "Acetazolamide or Placebo" or per institution standards as well as "Limited by Federal Law to Investigational Use Only." Drug products will be packaged in standard pharmacy containers with child resistant closures for outpatient use (e.g. amber HDPE bottles or prescription vials).

### 5.7.1 Blinding of Study

- Investigators, study staff in contact with patients, and subjects will be blinded. The research pharmacy will then dispense acetazolamide or placebo to the patient or study staff. Access to the randomization code will be strictly controlled by the research pharmacy and DMCC. Packaging, labeling, and appearance of the test and control treatments will be similar to maintain the blinding. Active drug concentrations will be prepared by the pharmacy prior to handoff to clinicians or patients/caretakers for administration. The study will proceed to open label continuation at Visit 5 (Week 40-56). During the study, the blind may be broken only in emergencies when knowledge of the patient's treatment group is necessary for further patient management. If the blind is broken for a subject, that individual will be removed from the blinded portion of the study. If a subject experiences an adverse event warranting unblinding procedures, the pharmacy will inform the physician of the prescribed treatment.

After all data are collected for the blinded portion of the study and all data cleaning is completed for these data, the data base for the blinded portion of the study will be locked and the study will be unblinded for analysis.

## **5.8 Receiving, Storage, Dispensing and Return**

### **5.8.1 Receipt of Drug Supplies**

Acetazolamide is an FDA-approved, commonly available drug. The research pharmacy will order the drug and prepare the proper dosage.

### **5.8.2 Storage**

- The research pharmacies are in secure locations only accessible to credentialed staff members with badge access.

### **5.8.3 Dispensing of Study Drug**

Regular study drug reconciliation will be performed to document drug assigned, drug dispensed, drug returns, and drug remaining. This reconciliation will be logged on the drug reconciliation form, signed, and dated by the study team/research pharmacist.

### **5.8.4 Return or Destruction of Study Drug**

In accordance with federal regulations (21CFR 312.62), all Investigators are required to keep accurate records showing final disposition of all investigational drugs and placebo.

Investigational drugs are to be used only in accordance with this protocol and under supervision of the Study Pharmacist or a duly designated person. An accurate drug disposition record will be kept at each site, specifying the amount dispensed and the date of dispensation. This inventory record must be available for inspection at any time. Copies of this record will be available for monitoring boards upon request.

After the study is completed, the Study Pharmacist must account for all drug used, unused and partially used. Unused study medication from the study site will be returned to either the investigator or Study Pharmacist and destroyed. Drug destroyed on site will be documented in the study files.

## 6 Study Procedures

Prior to participating in the study, written approval of the protocol and informed consent must be obtained from the IRB.

### Informed consent:

The investigator or designated study coordinator will explain the study to the patient and/or parents/guardian of the patient. Study purpose, procedures, risk, and benefits will be discussed. Patient/parents/guardians willingness and ability to meet the follow up requirements will be determined and written informed consent will be obtained. The investigator/study coordinator will also sign and date the consent form. The original informed consent form will be retained with the subject records; a copy will be provided to the patient/parent/guardian. Informed consent will be obtained prior to any procedures or data collection.

### Subject Identification:

Ethical and confidential research standards will be maintained. The minimum necessary protected health information will be used in study records. Computer records of data will be password protected behind institutional information technology security firewalls. All information will be treated with strict adherence to professional standards of confidentiality.

The following is a detailed list of study visits from screening to final follow-up and the required procedures/tests.

### 6.1 Visit 1 – Week 0

- Screening for eligibility
- Informed consent; no procedures will occur until informed consent and eligibility criteria are confirmed.
- Interview elements:
  - Medical history (past and current medical conditions, past surgical history)
  - Clinical history (history of present illness, any assessments)
  - Concomitant medication review
  - Ongoing therapies (physical therapy (PT), occupational therapy (OT), speech therapy (ST), feeding therapy (FT))
- Procedural elements:
  - Physical exam: Vital signs – temperature, systolic and diastolic blood pressures (mmHg), heart rate (beats/minute), respiratory rate (breaths/minute), Growth Data\* - length/height (cm), weight (kg), head circumference (HC in cm), Exam by systems – (normal/abnormal) brief neurologic exam, cardiovascular exam,

- abdominal exam, (HEENT) head ears eyes nose throat exam, dermatologic exam, pulmonary exam, musculoskeletal exam
- Mini-ICARS
- PATA
- NPCRS
- Blood collection\*\* (CBC (WBC, Hgb, Hct, Plt, % Neutrophils, % Lymphocytes, % Eosinophils, % Basophils, % Monocytes, % Bands, MCV, MCHC, MCH), electrolytes (Na, K, Cl, CO2), VBG (pH, pCO2, PO2, CO2, Base excess) or bicarbonate/CO2, liver function tests (AST, ALT, GGT, indirect and direct bilirubin, total protein, albumin, alkaline phosphatase, calcium, phosphorus, vitamin D, parathyroid hormone), coagulation factors (prothrombin time, coagulation factor XI, and antithrombin) kidney function tests (BUN, Creatinine), CTX, BSAP
- Urine collection (Urinalysis, urine calcium/creatinine ratio, urine protein/creatinine ratio, HCG for females)
- Survey given to families to complete and returned to site at or after visit by mail or electronically
  - PROMIS
- Performed after visit once inclusion and exclusion criteria are met and Mini-ICARS score established
  - Randomization
  - Dose Initiation – Investigational pharmacy to dispense to patient/caregiver by mail or in person at previously designated location by pharmacy. Investigator or pharmacist to instruct patient/caregiver regarding administration of drug or placebo via phone call, telehealth, or in person.

\*Growth data including length/height (cm), weight (kg), head circumference (HC in cm) will be measured or measured at home and reported by subjects at least every 12 weeks.

\*\*Total blood volume drawn will not exceed 5% of total blood volume of the child over 24-hour period, and 10% of total blood volume of the child over 8 weeks.

